#### **4.10.2 Deaths, Serious Adverse Events, and Other Significant Adverse Events**

Additional, significant AE summaries that will be provided are:

- Number and percentage of patients with serious AEs
- Number and percentage of patients with treatment-related serious AEs
- Number and percentage of patients with fatal AEs

All summaries will follow the same criteria as mentioned in [Section 14.10.1](#).

#### 4.10.3 Clinical Laboratory Evaluation

Local laboratories will be used for laboratory safety evaluations in this study. For a list of the parameters to be evaluated, see Table 1. Laboratory normal ranges will be provided by the local laboratory. For parameters where an NCI CTCAE v.5.0 scale exists, laboratory results will be graded according to the NCI CTCAE v.5.0 severity grade. For parameters for where an NCI CTCAE v.5.0 scale does not exist, an indicator of whether the value is below, within, or above the normal range will represent severity instead.

All laboratory values will be reported in SI units.

Summaries for each laboratory parameter will be presented by treatment group and visit. For by-visit summaries, the first non-missing assessment (including repeat assessments) recorded at each visit will be used. Optional laboratory parameters will not be summarized by dose group, only listed.

For laboratory values reported as a character value, such as <40, will be transformed into numerical values for summary reasons by following the specified guidelines. If a laboratory value is reported using the less than symbol, '<', 0.10 will be subtracted from the original numeric value. If a laboratory value is reported using the greater than symbol, '>', 0.10 will be added to the original numeric value.

A by-patient listing of all laboratory data, with abnormal values flagged, will be provided by treatment group. This listing will include patient identifier, age, gender, race, and visit, as well as laboratory reference ranges for each parameter.

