### 4.2 General Presentation Considerations

Baseline is the last available pre-treatment assessment. All assessments should have time collected. If time is not collected and date of assessment is the same as the *first dose date*, then assessment will be assumed to be collected prior to treatment unless schedule of assessments and protocol indicate planned collection is always after dosing.

Day-of-Discharge (DoD) is the day when patient is discharged from the hospital.

Durations are calculated as the stop date minus the start date plus one.

For elapsed time (e.g. time since the initial diagnosis), if the reference date is on or after the event date, then the elapsed time is the reference date minus the event date plus one. If the reference date is before the event date, then the elapsed time is the reference date minus the event date.

If more than one laboratory value is available for a given study day, the first valid observation will be used in summaries and all observations will be presented in listings. If it is not possible to determine which is the first measurement due to missing times, then the average of all measurements for that time point will be used as the value for that time point.

Continuous data will be summarized in terms of the mean, standard deviation (SD), median, minimum, maximum and number of observations, unless otherwise stated. Continuous data that are expected to be skewed will be presented in terms of the maximum, upper quartile, median, lower quartile, minimum and number of observations. The minimum and maximum will be reported to the same number of decimal places as the raw data recorded in the database. The mean, median, lower quartile and upper quartile will be reported to one more decimal place than the raw data recorded in the database. The SD will be reported to two more decimal places than the raw

---

data recorded in the database. In general, the maximum number of decimal places reported shall be four for any summary statistic.

The mixed model with repeated measurements /analysis of covariance model with treatment, country, participant's clinical status at Baseline and visit as the model term, and Baseline value as the covariate will be used to test for the significance of the treatment difference. Least square means, standard errors, 95% CIs and p-values will be presented.

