All the categorical variables including the primary endpoint will be summarized by treatment in terms of the number of patients providing data at the relevant time point (n), frequency counts and percentages. Binary primary endpoint: (progression to critical stage/death up to Day 14) will be analyzed by a Cochran-Mantel-Haenszel (CMH) stratified for the factors used in the stratified randomization. Treatment difference will be tested using a Cochran–Mantel–Haenszel (CMH) test stratified by 1) country and 2) participant's clinical status at Baseline. For the categorical endpoints, relative risk and its 95% CI will be presented.

Percentages will be presented to one decimal place. Percentages will not be presented for zero counts. Percentages will be calculated using n as the denominator. If sample sizes are small, the data displays will show the percentages, but any textual report will describe frequencies only.

Changes from baseline in categorical data will be summarized using shift tables where appropriate.

P-values greater than or equal to 0.001, in general, will be presented to three decimal places. P-values less than 0.001 will be presented as “<0.001”.

Confidence intervals will be presented to one more decimal place than the raw data.

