**Table 1 List of Laboratory Parameters**

Clinical Chemistry	Hematology
Blood urea nitrogen	White blood cell (WBC) count
Potassium	Red blood cell (RBC) count
Sodium	Hemoglobin
Aspartate Aminotransferase	Hematocrit
Total and Direct Bilirubin	Mean corpuscular volume
Creatinine	Mean corpuscular hemoglobin
Glucose non-fasting	Mean corpuscular hemoglobin concentration
Chloride	Red cell distribution width
Bicarbonate/CO2	Platelet
Serum Glutamic-Oxaloacetic Transaminase	Mean platelet volume
Alanine Aminotransferase	Methemoglobin
Serum Glutamic-Pyruvic Transaminase	
Alkaline phosphatase	
Lactate dehydrogenase	
Coagulation	
	Prothrombin Time
	International Normalized Ratio
	Activated Partial Thromboplastin Time

To assess Hy's Law, the number and percentage of patients with potentially clinically significant post-baseline elevations in hepatic parameters shown in Table 2 below will be summarized by treatment.

A listing of the patients with potentially clinically significant post-baseline hepatic elevations will be provided. The listing will contain all a subject's values for parameters meeting the criteria.

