#### 4.10.4 Vital Signs, Physical Findings and Other Observations Related to Safety

Summaries for each vital sign parameter will be presented by treatment arm and visit. Observed and change from baseline values in vital sign results will be analyzed using descriptive statistics. Change from baseline will only apply to post-baseline assessments.

Shifts in ECG results, from baseline to each post-baseline visit (where available) will be summarized by treatment arm. The maximum shift (across all visits) in ECG results from baseline will also be summarized by treatment arm.

By-patient listings of vital sign data, ECG results, and physical examination results will be provided by treatment arm.

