#### 4.10.3 Clinical Laboratory Evaluation

Local laboratories will be used for laboratory safety evaluations in this study. For a list of the parameters to be evaluated, see Table 1. Laboratory normal ranges will be provided by the local laboratory. For parameters where an NCI CTCAE v.5.0 scale exists, laboratory results will be graded according to the NCI CTCAE v.5.0 severity grade. For parameters for where an NCI CTCAE v.5.0 scale does not exist, an indicator of whether the value is below, within, or above the normal range will represent severity instead.

All laboratory values will be reported in SI units.

Summaries for each laboratory parameter will be presented by treatment group and visit. For by-visit summaries, the first non-missing assessment (including repeat assessments) recorded at each visit will be used. Optional laboratory parameters will not be summarized by dose group, only listed.

For laboratory values reported as a character value, such as <40, will be transformed into numerical values for summary reasons by following the specified guidelines. If a laboratory value is reported using the less than symbol, '<', 0.10 will be subtracted from the original numeric value. If a laboratory value is reported using the greater than symbol, '>', 0.10 will be added to the original numeric value.

Shifts in grade from baseline to the maximum shift(across all visits) will be summarized by treatment group.

A by-patient listing of all laboratory data, with abnormal values flagged, will be provided by treatment group. This listing will include patient identifier, age, gender, race, and visit, as well as laboratory reference ranges for each parameter.

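### Laboratory summaries use only the first value per day or visit, and the SAP plans no maximum or above-threshold table for methemoglobin

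*SAP*

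**What the plan says.** All references are to SAP version 2.0 unless stated.

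- **Rule per day.** Section 4.2: "If more than one laboratory value is available for a given study day, the first valid observation will be used in summaries". The remaining values are listed. If missing times hide which value came first, "the average of all measurements for that time point will be used as the value for that time point".
- **Rule per visit.** Section 4.10.3: "For by-visit summaries, the first non-missing assessment (including repeat assessments) recorded at each visit will be used". A repeat is therefore tabulated only if it is itself the first usable value.
- **Scope.** Table 1 lists methemoglobin under hematology, so both rules apply to it. Section 1 describes a nitric-oxide-generating product nebulized three times a day for up to 10 days. The revision history records a change of the methemoglobin threshold from 1% to 2%, without saying what that threshold governs.
- **Worst-case summaries for other data.** Section 4.10.3 counts patients with the post-baseline hepatic elevations defined in Table 2. For ECG, section 4.10.4 says: "The maximum shift (across all visits) in ECG results from baseline will also be summarized by treatment arm". Methemoglobin has neither kind of summary.
- **Other routes.** Section 4.2 keeps a general provision: "Changes from baseline in categorical data will be summarized using shift tables where appropriate". Section 4.10.1 tabulates adverse events by system organ class and preferred term. Section 4.10.3 provides a listing of all laboratory data with abnormal values flagged.

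**The concern.** Section 2.2 makes the overall safety profile of RESP301 a secondary objective. For a laboratory risk that the trial follows with its own threshold, the natural questions are how high each patient went and how many patients in each arm crossed the threshold. The planned laboratory tables answer neither. They describe one selected value per patient per visit, and the selection ignores later values on the same day, including a repeat taken because something looked wrong. A reader of the by-arm tables could see nothing unusual for methemoglobin while the relevant values sit in a listing.

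**Working it through.** The SAP states no figure on this point, so there is none to reproduce. The check is mainly a reading of the text, with small illustrations whose inputs are assumptions.

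**1. Where a second value on the same day goes.** Suppose, as an assumption, that a patient has 1.0% and then 2.5% on one study day.

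- Order known: the first value, 1.0%, is tabulated and 2.5% is listed.
- Order unknown: the average is tabulated, (1.0 + 2.5) / 2 = 1.75%.
- Per-patient maximum: 2.5%.

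Only the last exceeds the 2% named in the revision history.

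**2. What by-visit statistics show when nothing is discarded.** Section 3.1 randomizes 300 patients 2:1, so 300 × 2/3 = 200 receive RESP301. If all 200 have a value at a visit and one of them rises by 1.5 points (assumed), the visit mean moves by 1.5 / 200 = 0.0075 points. The visit maximum would show that a high value occurred. It would not give the number of patients above the threshold, and maxima at separate visits cannot be combined into a count of patients who ever crossed it.

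**3. How much within-day selection could matter.** Assume 3 × 10 = 30 administrations, one post-dose value after each, and an independent chance q that any value exceeds the threshold. The chance that a patient has at least one exceedance among n values is 1 − (1 − q)^n.

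| q | All 30 values | 10 first-of-day values |
|---|---|---|
| 0.5% | 14.0% | 4.9% |
| 1% | 26.0% | 9.6% |
| 2% | 45.5% | 18.3% |
| 5% | 78.5% | 40.1% |

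This is an illustration, not an estimate. Correlation between a patient's values narrows the gap. With one sample per day the two columns coincide. If the first value of a day is pre-dose, no post-dose value from that day enters the laboratory summaries.

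**4. Whether another planned output fills the gap.**

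- Hepatic counts and ECG shifts do not cover methemoglobin.
- The general shift-table provision is discretionary and names no maximum.
- Adverse event tables count a rise only if it is reported as an event, and the SAP has no rule that makes a threshold crossing an event.
- The listing shows every value but gives no comparison by arm.

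**The case against.** The strongest objection is that the loss depends on a sampling schedule that is not in the SAP. If methemoglobin is taken once per day and visit, after dosing, the first-value rule costs nothing. This stands, and it makes the within-day part of the point conditional. It does not touch step 2: even then, no planned laboratory table counts the patients who ever crossed the threshold.

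The rule is also a sound convention for by-visit means, because it stops unscheduled repeats from distorting comparisons between visits. That stands too, and the fix leaves it in place. Per-patient maxima rise with the number of samples, which may differ by arm in an open-label trial. This is a real drawback and is the reason for reporting sample counts.

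A reader might infer four stronger things that the documents do not support.

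- *Post-dose peaks are kept out of every summary.* Adverse event tables and discretionary shift tables remain, and a peak that is the first or only value of its day or visit is summarized.
- *The tabulated value is systematically the trough.* The SAP gives neither sampling times nor methemoglobin kinetics. A figure for the share of a rise left by the next morning would rest on an assumed half-life.
- *The Day 1 change is zero by construction.* Section 4.10.3 names no laboratory change-from-baseline table. Baseline is the last pre-treatment value while summaries take the first of the day, so the two need not coincide.
- *Version 2.0 removed a safeguard.* Version 1.0, section 4.10.3, did plan: "Shifts in grade from baseline to the maximum shift(across all visits) will be summarized by treatment group". But it had the same first-value rule in section 4.2, and its maximum ran across visits, so it is not shown that it would have caught a later value on the same day. It also worked on grades, and the SAP does not say whether methemoglobin is graded or where 2% would fall. Version 1.0 is superseded, so its removal is context and not an error.

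**Conclusion.** The point holds in a limited form. Version 2.0 restricts laboratory summaries to the first value per study day or visit, and it specifies neither a maximum post-baseline summary nor an above-threshold count for methemoglobin. A later or repeat high value, if one is sampled and not reported as an adverse event, would be visible only in listings. Independently of sampling times, the laboratory tables do not count patients who ever exceeded the threshold.

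The size cannot be fixed from the SAP. The within-day loss ranges from nothing (one sample per day and visit) to the order of the gaps illustrated above, under their stated assumptions. Efficacy conclusions are unaffected. This is a worthwhile and inexpensive improvement to a stated safety objective, and it brings methemoglobin into line with the worst-case treatment that hepatic parameters and ECG already receive.

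**What to change.** In section 4.10.3, exempt methemoglobin from the first-value and averaging rules for one safety table by treatment arm. Build it from all scheduled, repeat and unscheduled post-baseline values, and report:

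- the distribution of each patient's maximum post-baseline methemoglobin;
- the number and percentage of patients above the methemoglobin threshold defined in the protocol, cited by section;
- the number of methemoglobin samples per patient, so that a difference between arms in maxima can be read against a difference in sampling.

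Keep the first-value rule for by-visit means. The version 1.0 maximum-shift table need not be restored for this purpose and would not be sufficient alone.

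The cost is a short paragraph and one table shell. The values are already due to be listed, so no new data are needed. The remaining weakness is that maxima depend on sampling frequency; the sample counts disclose this but do not remove it.

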**REVISION HISTORY**

Version No.	Effective Date	Summary of Change(s)
1.0	16JUL2020	New document
2.0	05JAN2022	
1. Update SAP per new version of Protocol (Final, 16-Sep-2020; Amendment 3 (Version 4.0))
 
 
• Change of Title to include 'WHO grade 3 & 4'
 
• Modify Primary Objective/Endpoint for addition of WHO grade 3 or grade 4.
 
• Modify Secondary Objective/Endpoint for addition of WHO grade 3 or grade 4
 
• Change of wording accordingly to refer to use of supplemental oxygen 'if applicable' because WHO grade 3 do not require supplemental oxygen, so not all study patients will be using supplemental oxygen.
 
• Exclusion criterion 13 updated to specify that mHb >1% is exclusionary
 
• Amendment of Methb threshold from 1% to 2%
 
• Schedule of Activities: Changed description of oxygen measurements pre/post treatment to make clearer and remove repetition
 
• nebulization from 4 minutes to 8
 
 
2. Add/modify few abbreviation

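### SAP 4.10.3 shifts every censored laboratory result by a fixed 0.10, unscaled and with no stated order relative to SI conversion, so low reporting limits can yield zero or negative values

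*SAP*

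**What the plan says.** The rule is in SAP section 4.10.3, Clinical Laboratory Evaluation. Results that arrive as text with an inequality sign "will be transformed into numerical values for summary reasons by following the specified guidelines". The guidelines are two sentences. For results below a limit, "If a laboratory value is reported using the less than symbol, '<', 0.10 will be subtracted from the original numeric value". For results above a limit, "If a laboratory value is reported using the greater than symbol, '>', 0.10 will be added to the original numeric value". The only example is <40. Nothing restricts the rule by analyte, unit or number of reported decimals. SAP version 1.0 carries the same rule in its own section 4.10.3.

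Two other sentences of the section bear on it. "Local laboratories will be used for laboratory safety evaluations in this study", so units and reporting limits may differ between sites. And "All laboratory values will be reported in SI units", but whether that conversion comes before or after the 0.10 step is not stated.

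Table 1 lists the parameters covered. They sit on very different numerical scales and include "Total and Direct Bilirubin" and "Methemoglobin". Section 4.10.3 plans summaries per parameter, arm and visit. Section 4.2 includes the minimum in the summary of continuous data, both in the standard layout and in the one for skewed data.

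**The concern.** A constant offset is a reasonable stand-in for just below the limit only when the limit is large compared with the constant. At <40 that is so. For an analyte whose limit is a few tenths of a unit, the offset removes a large share of the limit. At a limit of 0.10 it removes all of it, and below 0.10 the substituted concentration is negative, which is impossible.

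The silence on the order of steps adds to this. If the 0.10 is taken from the number the local laboratory sent, the same censored result can enter the tables as different values, depending on the laboratory's unit. If it is taken after conversion, that dependence disappears, but the offset is still arbitrary relative to the SI unit chosen.

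At stake is the credibility of the laboratory safety tables. A zero or negative concentration would appear as the minimum of a by-arm, by-visit summary and would pull the mean down.

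**Working it through.** No figure in the plan needs reproducing except its example. The check is direct arithmetic.

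**Inputs from the SAP.** Offset 0.10, subtracted for `<L` and added for `>U` (4.10.3). Example <40 (4.10.3). Methaemoglobin and direct bilirubin are covered (Table 1). Methaemoglobin is put on a numerical scale only in the Revision History, where it is in percent; I use that for scale alone.

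**Assumptions, not in the SAP.** Reporting limits: 0.05 to 0.3 mg/dL for direct bilirubin and 0.1% to 2% for methaemoglobin. Bilirubin conversion: 17.1 umol/L per mg/dL.

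**Step 1: size of the shift.** Substituted value = L − 0.10. Shift relative to the limit = 0.10/L. The value is zero or below exactly when L ≤ 0.10.

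| Result | Substituted value | Shift as % of limit |
|---|---|---|
| <40 (SAP example) | 39.9 | 0.25% |
| <1 | 0.9 | 10% |
| <0.5 | 0.4 | 20% |
| <0.2 | 0.1 | 50% |
| <0.1 | 0 | 100% |
| <0.05 | −0.05 | 200% |

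For `>U` the value is U + 0.10. It cannot become negative, but its relative size, 0.10/U, depends on the unit in the same way.

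**Step 2: does the order matter?** Let k be the conversion factor. Offset first gives (L − 0.10) × k. Conversion first gives L × k − 0.10. The gap is 0.10 × (k − 1), which for bilirubin is 0.10 × 16.1 = 1.61 umol/L at every limit.

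| Direct bilirubin, assumed limit | Offset first (umol/L) | Conversion first (umol/L) |
|---|---|---|
| <0.05 mg/dL | −0.86 | 0.76 |
| <0.1 mg/dL | 0 | 1.61 |
| <0.2 mg/dL | 1.71 | 3.32 |
| <0.3 mg/dL | 3.42 | 5.03 |

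A laboratory reporting the second of these limits directly in SI units would send <1.71 umol/L (0.1 × 17.1), which becomes 1.61. With the offset first, two laboratories with the same limit therefore contribute 0 and 1.61. With conversion first, both contribute 1.61.

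**Step 3: methaemoglobin.** In percent, <2% becomes 1.9%, <1% becomes 0.9%, <0.5% becomes 0.4% and <0.1% becomes 0. Zero or below needs a limit of 0.1% or lower. If the value were held as a fraction, the whole assumed range (0.001 to 0.02) would lie below 0.10 and every substituted value would be negative; for example, 0.02 − 0.10 = −0.08.

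**The case against.** The strongest reply is that nothing shows the rule doing harm. The SAP gives no reporting limit or local unit for any analyte, so whether a single zero or negative value arises depends on facts outside it. The order may well be conversion first. In that case the local-unit problem vanishes and direct bilirubin stays positive at every limit tested. On the percent scale that the SAP uses for methaemoglobin, <1% becomes 0.9%, which is trivial. Section 4.2 already gives medians throughout, and quartiles in place of means where skew is expected. Listings carry all observations. The hepatic criteria in Table 2 concern elevations, which a 0.10 shift in a low result would not trigger.

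Most of this stands, and it limits the point to what the rule can do. It does not remove the defect. The order is unstated, and the closing words of the rule can be read as the number the laboratory sent. Under either order, any limit of 0.10 or lower in the unit used still gives an impossible value, and the printed minimum would show it.

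A reader might infer more: that methaemoglobin summaries will be badly distorted, that the error rivals the percent thresholds in the Revision History, or that rises from baseline will be inflated. The SAP does not support these. A large methaemoglobin error needs the fraction scale, which the SAP does not use. Nothing says methaemoglobin is the analyte most often censored. The substitution is for summaries only, and no methaemoglobin analysis is tied to those thresholds. Section 4.10.3 does not specify change from baseline for laboratory values; section 4.10.4 does so for vital signs.

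**Conclusion.** The point holds as a minor defect. The SAP fixes one absolute offset for all analytes and units and leaves its order relative to SI conversion open. By arithmetic alone, the shift is 0.25% of the limit at <40, 50% at <0.2 and 100% at <0.1, and the result is zero or negative whenever the limit is 0.10 or lower in the unit used.

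The bilirubin contrast (0 against about 1.6 umol/L) rests on an assumed limit of 0.1 mg/dL and an assumed factor of 17.1. The zero, and the dependence on the local unit, arise only if the offset precedes conversion. For methaemoglobin, zero or negative values need a limit of 0.1% or less in percent, or 0.10 or less if held as a fraction.

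The effect is confined to descriptive laboratory summaries. The primary analysis and the Table 2 hepatic criteria are not touched.

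**What to change.** Replace the two offset sentences in section 4.10.3 with a rule along these lines:

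- Convert the reporting limit to SI units first.
- For summaries, set `<x` to a value scaled to the limit or to its reporting precision (for example x/2, or x itself), and set `>x` to x.
- Never substitute a value below zero.
- Footnote the number of censored values for each parameter.

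The choice among these conventions is a matter of preference; what matters is that the value scales. With x/2 or x, the result no longer depends on the unit, since (x/2) × k = (x × k)/2. A rule based on the last reported decimal does not have that property, so the order of steps should be written down in any case.

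The cost is one sentence in the SAP and a change to one derivation. No new data are needed.
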